3.6.4.3 Overall Improvement and Overall Improvement/Stability

Overall improvement rate will be analyzed, which is defined as the proportion of participants who have achieved an improvement as defined in Section 3.4.3 PRO Endpoints. Stratified Miettinen and Nurminen’s method will be used for comparison of the overall improvement rate between the treatment groups. The difference in overall improvement rate and its 95% CI from the stratified Miettinen and Nurminen’s method with strata weighting by sample size will be provided. The stratification factors used for randomization (See Section 7.3.1 in protocol) will be applied to the analysis.

The point estimate of overall improvement rate will be provided by treatment group, together with 95% CI using exact binomial method by Clopper and Pearson [5]. The same method will be used to analyze overall improvement/stability rate, which is defined as the proportion of participants who have achieved improvement/stability as defined in Section 3.4.3 PRO Endpoints.

3.6.4.4 Analysis Strategy for Key PRO Endpoints

Endpoint/Variable	Statistical Method	Analysis Population	Missing Data Approach
Mean change from baseline in – EORTC QLQ-C30 
 • Global health status/QoL • Functioning scale • Symptom scale – FKSI-DRS – EQ-5D VAS	cLDA model	FAS	Model-based.
Overall improvement and overall improvement/stability in – EORTC QLQ-C30 
 • Global health status/QoL • Physical functioning – FKSI-DRS	Stratified Miettinen and Nurminen method	FAS	Participants with missing data are considered not achieving improvement/stability.

Abbreviations: cLDA = constrained longitudinal data analysis, FAS = full analysis set, QoL = quality of life.

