9.2.2.3 Functional Assessment of Cancer Therapy Kidney Symptom Index – Disease-Related Symptoms

The FKSI-DRS is a patient-reported instrument that measures whether the participant has experienced any of the following 9 kidney cancer-related symptoms: lack of energy, fatigue, weight loss, pain, bone pain, shortness of breath, cough, fever, or blood in the urine [Cella, D., et al 2007]. Each item is scored by using the following 5 response categories: 0, not at all; 1, a little bit; 2, somewhat; 3, quite a bit; and 4, very much. Responses to all FKSI-DRS items are summed to generate a summary symptom score ranging from 0 to 36, with higher scores indicating improved (more favorable) symptom status. The FKSI-DRS is a reliable, valid, and responsive brief index of the most important symptoms associated with advanced kidney cancer [Cella, D., et al 2007].

If, at the time of first dose of study treatment, the translated version of the FKSI-DRS – one of the PRO measures – is not available for that language/country, and it cannot be completed by the participant at Cycle 1, Day 1, then the FKSI-DRS will not be required for this participant at any point of the study. The other study PRO measures must be completed as scheduled.

Note: For some sites, the translated FKSI-DRS might become available after study startup and should be administered to participants at their time of first dose of study treatment; for some sites, the FKSI-DRS translation might not be available for the entire duration of the study. Missing FKSI-DRS for such a reason will not be considered a protocol deviation.

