3.5.3 PRO Analysis Population

The PRO analyses are based on the PRO full analysis set (FAS) population, defined as subjects who have at least one PRO assessment available and have received at least one dose of the study medication. Participants will be analyzed in the treatment group to which they are randomized.

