3.6.4.1 PRO compliance summary

Completion and compliance of EORTC QLQ-C30, FKSI-DRS and EQ-5D by visit and by treatment will be described. Numbers and percentages of complete and missing data at each visit will be summarized. An instrument is considered complete if at least one valid score is available according to the missing item rules outlined in the scoring manual for the instrument.

Completion rate of treated participants (CR-T) at a specific time point is defined as the number of treated participants who complete at least one item over the number of treated participants in the PRO analysis population.

$$CR-T = \frac{\text{Number of treated participants who complete at least one item}}{\text{Number of treated participants in the PRO analysis population}}$$

The completion rate is expected to shrink in the later visit during study period due to the participants who discontinued early. Therefore, another measurement, compliance rate of eligible participants (CR-E) will also be employed as the support for completion rate. CR-E is defined as the number of treated participants who complete at least one item over number of eligible participants who are expected to complete the PRO assessment, not including the participants missing by design such as death, discontinuation, translation not available.

$$CR-E = \frac{\text{Number of treated participants who complete at least one item}}{\text{Number of eligible participants who are expected to complete}}$$

The reasons of non-completion and non-compliance will be provided in supplementary table:

- Completed as scheduled
- Not completed as scheduled
- Off-study: not scheduled to be completed.

In addition, reasons for non-completion as scheduled of these measures will be collected using “miss_mode” forms filled by site personnel and will be summarized in table format. The

schedule (study visits and estimated study times) and mapping of study visit to analysis visit for PRO data collection is provided in [Table 4](#).

Table 4 PRO Data Collection Schedule and Mapping of Study visit to Analysis Visit

Study Week	Week 0 (Baseline)	Week 12	Week 24 to Week 36 (Every 12 weeks)	Week 48	Week 52	Week 104 to Week 120 (Every 16 weeks)
Study Day	1	85	Week number *7+1	337	365	Week number *7+1
Day Range	<=1	[2, 126]	[Week number*7-41, week number*7+42]	[295, 351]	[352, 546]	[Week number*7-181, week number*7+182]

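### Participants exempted from the FKSI-DRS for lack of a translation count as non-responders, which lowers the exploratory FKSI-DRS responder rates and shrinks their expected difference toward zero

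*Combined protocol and SAP*

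**What the plan says.** Protocol 9.2.2.3 deals with languages for which no FKSI-DRS translation is ready. If the participant cannot complete it at Cycle 1, Day 1 for that reason, "then the FKSI-DRS will not be required for this participant at any point of the study". The remaining questionnaires are unaffected: "The other study PRO measures must be completed as scheduled". The protocol adds that a translation may never reach some sites, and it describes the resulting gap in these words: "Missing FKSI-DRS for such a reason will not be considered a protocol deviation".

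sSAP 3.5.3 defines one PRO full analysis set (FAS) for all instruments: "subjects who have at least one PRO assessment available and have received at least one dose of the study medication".

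sSAP 3.6.4.3 describes the overall improvement rate as "defined as the proportion of participants who have achieved an improvement as defined in Section 3.4.3 PRO Endpoints", and treats improvement/stability in the same way. sSAP 3.6.4.4 applies the FAS to both rates for the FKSI-DRS, with the rule "Participants with missing data are considered not achieving improvement/stability".

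sSAP 3.6.4.1 shows that the sponsor knew of this group. The denominator of the compliance rate CR-E is the participants expected to complete the assessment, "not including the participants missing by design such as death, discontinuation, translation not available". Nothing comparable is said about the responder denominators.

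**The concern.** Counting missing data as failure is a defensible conservative rule for someone who was due to complete a questionnaire and did not. It makes little sense for someone who was never given it. An exempt participant has no baseline FKSI-DRS score and so can never meet a definition based on confirmed change from baseline (sSAP 3.4.3.2). The failure is fixed by language and country, not by symptoms.

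The FKSI-DRS improvement and improvement/stability rates, their exact intervals and the stratified Miettinen-Nurminen difference would then partly measure translation coverage. A benefit of pembrolizumab on this scale would be understated in expectation, and so would a deficit.

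**Working it through.** The documents give no FKSI-DRS responder rate, no PRO sample size and no count of untranslated participants, so there is no planned figure to reproduce. The effect is algebraic.

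**Status of an exempt participant, step by step**

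1. No FKSI-DRS at any visit (protocol 9.2.2.3).
2. The EQ-5D-5L and QLQ-C30 are still due, so one completed assessment plus one dose puts the participant in the FAS (sSAP 3.5.3).
3. The FKSI-DRS responder analyses use that FAS (sSAP 3.6.4.4).
4. Missing counts as not achieved (sSAP 3.6.4.4), so the participant adds 1 to the denominator and 0 to the numerator.

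**Effect on rates and difference**

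Let u be the untranslated share of the FAS, and p_T and p_C the responder rates among those asked. Translation status is settled at first dose in a blinded randomized trial, so u is the same in both arms in expectation.

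- Estimated rate in each arm: (1 − u) × p
- Expected difference: (1 − u) × (p_T − p_C)

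With assumed improvement/stability rates of 85% and 80%:

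| u | Rates under the plan | Difference (points) |
|---|---|---|
| 0% | 85.0% vs 80.0% | 5.0 |
| 5% | 80.8% vs 76.0% | 4.8 |
| 10% | 76.5% vs 72.0% | 4.5 |
| 20% | 68.0% vs 64.0% | 4.0 |

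With the arms reversed, −5.0 becomes −4.0 at u = 20%, again closer to zero.

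**Stratification**

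The planned difference uses sample-size weights w_s, so its expectation is the sum over strata of w_s(1 − u_s)d_s, where d_s is the difference among those asked in stratum s. This equals (1 − u)d if the u_s are unrelated to the d_s, for example if d_s is the same in every stratum. Otherwise (1 − u) is only approximate. Stratifying does not remove the effect: US status is a stratum only within M0 (protocol 7.3.1), and the weights count unasked participants in full.

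**Precision**

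Assume 495 per arm (990/2, everyone in the FAS), u = 20% and unpooled binomial standard errors.

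- 87% vs 80% among those asked. Under the plan, the difference is 69.6 − 64.0 = 5.6 points, SE = √[(0.696×0.304 + 0.640×0.360)/495] = 2.99 points, 95% CI −0.26 to 11.46. Among the 396 per arm who were asked, it is 7.0 points, SE = √[(0.87×0.13 + 0.80×0.20)/396] = 2.63 points, 95% CI 1.85 to 12.15.
- 20% vs 15% among those asked. Under the plan, 4.0 points (−0.32 to 8.32). Among those asked, 5.0 points (−0.28 to 10.28). The ratio of estimate to SE hardly moves: 1.82 against 1.86.

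The loss of precision therefore matters mainly when the true rates are high.

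**Chance imbalance**

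At u = 20% the between-arm gap in u has an SD of √(2×0.2×0.8/495) = 2.5 points. With u of 22% vs 18%, the 87% vs 80% case gives 0.87×0.78 − 0.80×0.82 = 2.3 points. With the imbalance reversed it gives 0.87×0.82 − 0.80×0.78 = 8.9 points. Attenuation holds in expectation, not in every realized trial.

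**The case against.** Four arguments on the other side carry weight.

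**The rates are exploratory.** sSAP 3.4.3.2 lists the proportions as exploratory, and 3.6.4 provides nominal p-values with no formal testing. This stands, and it limits the importance of the point. A reader might infer that a secondary endpoint is compromised. The documents do not support that: the secondary FKSI-DRS endpoint is mean change from baseline (3.4.3.1), analysed by cLDA with model-based handling of missing data, so the missing-as-failure rule does not reach it.

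**The effect may be nil.** Protocol 9.2.2.3 says only that translations might arrive late or not at all. This also stands: u is unknown, and at u = 5% the illustrated difference moves by only about a quarter of a point.

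**The FAS may be meant per instrument.** The phrase about having one PRO assessment could be read that way, and the problem would then disappear. The text does not say so, and sSAP 3.6.4.1 points the other way. The CR-T denominator is the PRO analysis population, and CR-E then removes those without a translation. In an instrument-specific set, participants with no FKSI-DRS at all would already be gone and that removal would be largely redundant.

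**The gap will be visible.** Compliance is reported by visit and arm, and reasons for non-completion are tabulated. This discloses the gap but does not correct the responder rates.

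A reader might also infer that the rule spoils a comparison with the QLQ-C30 responder rates. No such comparison is planned, and the thresholds differ in any case (3 points against 10).

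**Conclusion.** The point holds, and it is minor. Read literally, the plan makes every participant exempted under protocol 9.2.2.3 an automatic FKSI-DRS non-responder. This lowers the exploratory improvement and improvement/stability rates in both arms. In expectation it also shrinks their difference toward zero, by about (1 − u) if the untranslated share is unrelated to the stratum effects. Both u and the true rates are assumptions here; if u is zero there is no bias.

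A reader might infer that the difference is simply too low, to the disadvantage of pembrolizumab. That does not follow. If pembrolizumab does worse on this scale, the same rule understates the deficit, and chance imbalance in u can move a single result either way. The QLQ-C30 responder rates are unaffected, and no formal test or alpha depends on the affected rates.

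**What to change.** In sSAP 3.5.3 and 3.6.4.4, state that participants exempted from the FKSI-DRS under protocol 9.2.2.3 are excluded from the FKSI-DRS responder denominators. This makes the analysis set instrument-specific for that purpose. Take over only the translation exclusion from CR-E, not its exclusions for death and discontinuation, and keep missing as failure for everyone who was required to complete the instrument. Report the number exempted by arm.

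The exemption is settled by language and country at first dose under blinding, so the exclusion does not select on outcome. The cost is one sentence and a flag, plus a FKSI-DRS denominator smaller than the QLQ-C30 one, with rates that describe only participants for whom a translation existed.

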3.7 INTERIM ANALYSES

Treatment-level results of the interim analysis will be provided by the unblinded statistician to the external data monitoring committee (eDMC). Limited additional Sponsor personnel may be unblinded to the treatment level results of the interim analysis (analyses), if required, in order to act on the recommendations of the eDMC. The extent to which individuals are unblinded with respect to results of interim analyses will be documented by the unblinded statistician.

The eDMC will serve as the primary reviewer of the unblinded results of the DFS and OS at interim analyses and will make recommendations for discontinuation of the study or modification to an Executive Oversight Committee (EOC) of the Sponsor. Depending on the recommendations of the eDMC, the Sponsor may prepare a regulatory submission. If the eDMC recommends modifications to the design of the protocol or discontinuation of the study, the EOC may be unblinded to results at the treatment level in order to evaluate and direct the Sponsor protocol team as to the appropriate actions to be taken on these recommendations. Additional logistical details, revisions to the above plan, and data monitoring guidance will be provided in the DMC Charter.

Prior to final study unblinding, the unblinded statistician and unblinded scientific programmer will not be involved in any discussions regarding modifications to the protocol, statistical methods, identification of protocol deviations, or data validation efforts after the interim analyses.

If the trial is positive at an interim analysis for primary endpoint DFS, additional analyses, including but not limited to the protocol-specified final analysis, may be carried out for exploratory purpose or upon regulatory request.

3.7.1 Safety Interim Analyses

The eDMC has responsibility for assessment of overall risk:benefit. Periodic safety monitoring will be specified in the eDMC charter with input from the eDMC members. When prompted by safety concerns, the eDMC can request efficacy data to assess the overall risk: benefit to study participants. Any eDMC recommendation will be communicated to the Executive Oversight Committee (EOC) as agreed to in the eDMC charter.

3.7.2 Efficacy Interim Analyses

Three interim analyses are planned in addition to the final analysis for this trial. In this study, the futility bounds are non-binding. Results of the interim analyses (IA) will be reviewed by an eDMC. If both DFS and OS null hypotheses are rejected prior to the final analysis, the eDMC may recommend stopping the trial early for efficacy. At each IA, the eDMC may also recommend stopping the trial early for futility. Details on how the above planned analyses are incorporated into establishing statistical significance and the boundaries with regard to efficacy and futility are discussed further in Section 3.8, Multiplicity.

The analyses planned, endpoints evaluated and drivers of the timing are summarized in [Table 5](#).

Table 5 Analyses Planned, Endpoints Evaluated and Drivers of Timing

Analysis	Endpoint(s)	Timing
IA1	DFS, OS	Enrollment complete and approximately 265 DFS events by investigator assessment have occurred and a minimum follow-up (time from last participant randomized to IA1) of 12 months is achieved.
IA2	DFS, OS	332 DFS events by investigator assessment; if DFS rejected before IA2, timing driven by 132 OS events
IA3	OS	172 OS events
FA	OS	200 OS events

3.8 MULTIPLICITY

3.8.1 Multiplicity Control for Efficacy Analyses

The trial uses the method of Maurer and Bretz [6] to provide strong multiplicity control for multiple hypotheses as well as interim analyses. Figure 1 shows the initial one-sided α -allocation for each hypothesis in the ellipse representing the hypothesis. The weights for reallocation from each hypothesis to the others are represented in the boxes on the lines connecting hypotheses. This is further explained below.

[figure not shown]

Figure 1 Multiplicity Graph for Type I Error Control of Study Hypotheses

If the DFS null hypothesis is rejected at the 2.5% level, then the OS null hypothesis may be formally evaluated for statistical significance at the 2.5% level. For each endpoint, group sequential methods will be used to adjust for the interim and final analyses planned. If the DFS null hypothesis is rejected at an interim or final analysis, each OS interim and final analysis test may be compared to its rejection boundary for formal testing. For instance, the OS hypothesis will not be formally evaluated for statistical significance until the DFS null hypothesis is rejected.

For DFS, the information fraction at each analysis will be based on the final planned number of 332 events. A Lan-DeMets O’Brien-Fleming spending approximation α -spending function is used to set efficacy bounds. Non-binding futility spending is done by controlling the

probability of crossing the futility bound under the null hypothesis (total of $1-\alpha=97.5\%$); a Hwang-Shih-DeCani (HSD) spending function with $\gamma=-6$ is used to set testing boundaries at each analysis.

For OS, the information fraction at each analysis will be based on the final planned number of 200 deaths. A Lan-DeMets O’Brien-Fleming spending approximation α -spending function is used to set efficacy bounds. As with DFS, non-binding futility spending is done by controlling the probability of crossing the futility bound under the null hypothesis (total of $1-\alpha=97.5\%$); an HSD spending function with $\gamma=-6$ is used to set testing boundaries at each analysis.

Bounds at the expected number of events for each hypothesis at each analysis of DFS and OS are shown in Table 6 and Table 7, respectively. If the actual number of DFS or OS events at the interim and final analyses differs from those specified in the table, the bounds will be updated using this spending function evaluated at the observed information fraction (fraction of observed over expected final events) at each analysis.

Table 6 Boundary Properties for Planned Interim and Final Analyses for DFS

Analysis	Value	Efficacy	Futility[†]
IA1: 80% (First Interim for DFS) N: 990 Events: 265 Month: 39	Z p (1-sided) HR at bound P(Cross) if HR=1 P(Cross) if HR=0.67	2.2504 0.0122 0.7584 0.0122 0.8402	-0.5476 0.7080 1.0696 0.2920 0.0001
IA2: (Final Analysis for DFS) N: 990 Events: 332 Month: 50	Z p (1-sided) HR at bound P(Cross) if HR=1 P(Cross) if HR=0.67	2.0249 0.0214 0.8005 0.0250 0.9490	2.0249 0.0214 0.8005 0.9750 0.0510
IA = Interim Analysis. [†] : Futility boundary is non-binding.			

Table 7 Boundary Properties for Planned Interim and Final Analyses for OS

Analysis	Value	Efficacy	Futility†
IA1: 47% (First Interim for OS) N: 990 Events: 94 Month: 39	Z p (1-sided) HR at bound P(Cross) if HR=1 P(Cross) if HR=0.67	3.0679 0.0011 0.5305 0.0011 0.1280	-1.7717 0.9618 1.4421 0.0382 0.0001
IA2: 66% (Second Interim for OS) N: 990 Events: 132 Month: 50	Z p (1-sided) HR at bound P(Cross) if HR=1 P(Cross) if HR=0.67	2.5455 0.0055 0.6416 0.0058 0.4033	-1.1786 0.8807 1.2281 0.1247 0.0003
IA3: 86% (Third Interim for OS) N: 990 Events: 172 Month: 63	Z p (1-sided) HR at bound P(Cross) if HR=1 P(Cross) if HR=0.67	2.2023 0.0138 0.7143 0.0157 0.6688	-0.2090 0.5828 1.0324 0.4195 0.0025
Final N: 990 Events: 200 Month: 72	Z p (1-sided) HR at bound P(Cross) if HR=1 P(Cross) if HR=0.67	2.0534 0.0200 0.7476 0.0250 0.7930	2.0534 0.0200 0.7476 0.9750 0.2070
IA = Interim Analysis. †: Futility boundary is non-binding.			

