
Interim and Final Analyses
	
Three interim analyses are planned for the study (one interim analysis for DFS and 3 interim analyses for OS). Results will be reviewed by an external data monitoring committee. Details are provided in Section 10.7.
 
 • IA1 
 o Purpose: Interim analysis for DFS and OS. o Timing: When at least 265 disease recurrence events by investigator assessment have accrued and a minimum follow-up (time from last participant randomized to IA1) of 12 months is achieved. Approximately 94 OS events are expected at this time. • IA2 
 o Purpose: Final analysis for DFS and interim analysis for OS o Timing: Final analysis of DFS when approximately 332 DFS events by investigator assessment have accrued if DFS is not rejected at IA1, Approximately 132 OS events are expected at this time. • IA3 
 o Purpose: Interim analysis for OS o Timing: When approximately 172 OS events have accrued, • Final analysis (FA) 
 o Purpose: Final analysis for OS o Timing: When approximately 200 OS events have accrued,

Multiplicity
	
The overall Type I error rate is strongly controlled at 2.5% (1-sided) with a fixed sequence testing procedure to test DFS at alpha level of 2.5% (1-sided) first and pass the alpha to OS if the hypothesis test of DFS is declared successful. A group sequential approach will be used to allocate alpha between the interim and final analyses. The study will be considered a success if DFS is demonstrated to be statistically significant under multiplicity control. Note that if the statistical criterion for success for DFS is met at an IA, a regulatory application may be submitted based on DFS for a full approval consideration and the study could still continue for OS.

Sample Size and Power
	
The sample size was planned for 950, but the following power calculations are based on 990, which is a number more in line with the actual final number of randomized subjects. DFS is the primary endpoint for this study. The expected median DFS time in the control group is 45 months; based on 332 events and a Poisson mixture cure rate model with assumed cure rate of 0.3, the study has 95% power to detect a hazard ratio of 0.67 (pembrolizumab versus placebo) at alpha = 2.5% (1-sided).

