10.8 Multiplicity

10.8.1 Multiplicity Control for Efficacy Analyses

The trial uses the method of Maurer and Bretz (2013)[Maurer, W. 2013] to provide strong multiplicity control for multiple hypotheses as well as interim analyses. [Figure 2](#) shows the initial one-sided α -allocation for each hypothesis in the ellipse representing the hypothesis. The weights for reallocation from each hypothesis to the others are represented in the boxes on the lines connecting hypotheses. This is further explained below.

Figure 2 Multiplicity Graph for Type I Error Control of Study Hypotheses

Abbreviations: DFS = disease-free survival; OS = overall survival

If the DFS null hypothesis is rejected at the 2.5% level, then the OS null hypothesis may be formally evaluated for statistical significance at the 2.5% level. For each endpoint, group sequential methods will be used to adjust for the interim and final analyses planned. If the DFS null hypothesis is rejected at an interim or final analysis, each OS interim and final analysis test may be compared to its rejection boundary for formal testing. For instance, the OS hypothesis will not be formally evaluated for statistical significance until the DFS null hypothesis is rejected.

For DFS, the information fraction at each analysis will be based on the final planned number of 332 events. A Lan-DeMets O'Brien-Fleming spending approximation α -spending function is used to set efficacy bounds. Nonbinding futility spending is done by controlling the probability of crossing the futility bound under the null hypothesis (total of $1-\alpha=97.5\%$); a HSD spending function with $\gamma = -6$ is used to set testing boundaries at each analysis.

For OS, the information fraction at each analysis will be based on the final planned number of 200 deaths. A Lan-DeMets O'Brien-Fleming spending approximation α -spending function is used to set efficacy bounds. As with DFS, nonbinding futility spending is done by controlling the probability of crossing the futility bound under the null hypothesis (total of $1-\alpha=97.5\%$); an HSD spending function with $\gamma = -6$ is used to set testing boundaries at each analysis.

Bounds at the expected number of events for each hypothesis at each analysis of DFS and OS are shown in [Table 14](#) and [Table 15](#), respectively. Bounds will be adjusted according to the actual number of events at each analysis.

Table 14 Boundary Properties for Planned Interim and Final Analyses for DFS

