
Interim and Final Analyses
	
Three interim analyses are planned for the study (one interim analysis for DFS and three interim analyses for OS). Results will be reviewed by an external data monitoring committee. Details are provided in Section 10.7.
 
 • First Interim Analysis (IA1) 
 o Purpose: Interim analysis for DFS and OS. o Timing: When approximately 265 disease recurrence events by investigator assessment have accrued and a minimum follow-up (time from last participant randomized to IA1) of 12 months is achieved. Approximately 94 OS events are expected at this time. • Second Interim Analysis (IA2) 
 o Purpose: Final analysis for DFS and interim analysis for OS o Timing: Final analysis of DFS when approximately 332 DFS events by investigator assessment have accrued if DFS is not rejected at IA1, Approximately 132 OS events are expected at this time. • Third Interim Analysis (IA3) 
 o Purpose: Interim analysis for OS o Timing: When approximately 172 OS events have accrued, • Final analysis (FA) 
 o Purpose: Final analysis for OS o Timing: When approximately 200 OS events have accrued,

Multiplicity
	
The overall Type I error rate is strongly controlled at 2.5% (1-sided) with a fixed sequence testing procedure to test DFS at alpha level of 2.5% (1-sided) first and pass the alpha to OS if the hypothesis test of DFS is declared successful. A group sequential approach will be used to allocate alpha between the interim and final analyses. The study will be considered a success if DFS is demonstrated to be statistically significant under multiplicity control. Note that if the statistical criterion for success for DFS is met at an IA, a regulatory application may be submitted based on DFS for a full approval consideration and the study could still continue for OS.

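### The sSAP's bound-update rule, as worded, leaves part of the 2.5% alpha unspent if a final analysis falls short of 332 DFS events or 200 deaths

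*Combined protocol and SAP*

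**What the plan says.** Both documents use a Lan-DeMets O'Brien-Fleming-type function for efficacy in each endpoint ("spending approximation α -spending function is used to set efficacy bounds"). Both fix the information denominators at the planned totals. In protocol Section 10.8.1, which sSAP 3.8.1 repeats: "For DFS, the information fraction at each analysis will be based on the final planned number of 332 events", and "For OS, the information fraction at each analysis will be based on the final planned number of 200 deaths".

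The documents differ in how they describe an update. Protocol 10.8.1 says only this: "Bounds will be adjusted according to the actual number of events at each analysis". sSAP 3.8.1 is specific. Its rule is triggered as follows: "If the actual number of DFS or OS events at the interim and final analyses differs from those specified in the table". The bounds are then recomputed with the spending function "evaluated at the observed information fraction (fraction of observed over expected final events) at each analysis".

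Neither document says that the final analysis spends all remaining alpha, or that the fraction is set to 1 or capped at 1 there. The overall claim, in sSAP 3.1 and in the protocol's SAP summary, is this: "The overall Type I error rate is strongly controlled at 2.5% (1-sided) with a fixed sequence testing procedure". Both summaries describe the final triggers as approximate counts of 332 and 200. The timing tables (protocol Table 13, sSAP Table 5) list the same counts without that qualifier.

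**The concern.** At an interim analysis, observed over planned events is the right argument for the spending function. At the final analysis there is no later look to use any alpha held back. If the database closes with fewer events than planned, the rule evaluates the function at a fraction below 1, and the difference from 0.025 is lost.

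The effect is a stricter final bound and less power than the 2.5% level allows. It matters more for OS, where planned power is only about 79% and the last look is the last chance to reject. A final one-sided p of 0.018 at 190 deaths would fail under the sSAP wording, although 2.5% control permits a bound of 0.0213. Choosing full spending only after the final count is known would depart from the written rule at a confirmatory test and could be challenged.

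**Working it through.** **Inputs.** One-sided alpha is 0.025. DFS has looks at 265 and 332 events. OS has looks at 94, 132, 172 and 200 deaths (sSAP 3.8.1, Tables 6 and 7). The hazard ratio is 0.67 with 1:1 allocation (sSAP 3.9). OS power is conditional on the DFS null having been rejected, as in the plan.

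**Method.** The spending function is α(t) = 2[1 − Φ(z/√t)], where z = 2.2414 is the upper 1.25% normal quantile and t is observed over planned events. Bounds and power come from numerical integration of the group-sequential normal process, with information equal to events/4 and drift −ln(0.67). The non-binding futility bounds are ignored.

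**Reproducing the plan.**
- DFS with t = 0.80 at IA1: Z = 2.2504 and 2.0250, p = 0.0122 and 0.0214, cumulative alpha 0.0250 (Table 6: 2.2504 and 2.0249, 0.0122 and 0.0214, 0.0250). Using 265/332 = 0.798 instead gives p = 0.0121 and 0.0215; that version is used below.
- OS: Z = 3.0679, 2.5456, 2.2023 and 2.0534; p = 0.0011, 0.0055, 0.0138 and 0.0200 (Table 7 agrees, with Z within 0.0001).
- Power: 95.1% for DFS and 79.7% for OS, against 94.9% and 79.3% in the tables. These differences are small and do not affect the comparisons below.

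**Deviation at the interim only.** With DFS IA1 anywhere from 250 to 300 events and the final at 332, cumulative alpha is 0.0250. The rule works as intended there.

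**Shortfall at the final analysis.**
- OS at 190 deaths: t = 190/200 = 0.95; 2.2414/√0.95 = 2.300; α = 0.0215. IA3 has already used 0.0157, so 0.0215 − 0.0157 = 0.0058 is left for the last look, against 0.0250 − 0.0157 = 0.0093 under full spending.
- DFS at 315 events: t = 315/332 = 0.949; 2.2414/√0.949 = 2.301; α = 0.0214. The last look gets 0.0214 − 0.0121 = 0.0093, against 0.0250 − 0.0121 = 0.0129.

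| Final count | Cumulative alpha, sSAP rule | Final p-bound, sSAP rule / full spend | Power, sSAP rule / full spend |
|---|---|---|---|
| OS 196 | 0.0236 | 0.0186 / 0.0205 | 78.1% / 79.0% |
| OS 190 | 0.0215 | 0.0165 / 0.0213 | 75.6% / 78.0% |
| DFS 325 | 0.0235 | 0.0200 / 0.0218 | 94.4% / 94.7% |
| DFS 315 | 0.0214 | 0.0179 / 0.0223 | 93.2% / 94.2% |

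**More events than planned.** If the function is held at 0.025 once t reaches 1, cumulative alpha is exactly 0.0250 (checked at 340 and 350 DFS events and at 205 and 210 deaths). If the formula is instead extrapolated past t = 1, it gives 0.0288 at 349 DFS events and 0.0287 at 210 deaths.

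**The case against.** The best defence is that the wording is loose rather than deliberate. In Tables 6 and 7 the efficacy and futility bounds coincide at the last look, and the null crossing probabilities add to 0.0250 + 0.9750 = 1, which is what full spending produces. Applying the sSAP rule literally to both functions at 315 DFS events would spend 0.0214 for efficacy and 0.7165 for futility. That leaves 1 − 0.0214 − 0.7165 = 0.262 of the null probability with no decision at a final analysis, which nobody would intend. This is good evidence of intent, but it does not supply the missing instruction, and the written rule names the final analysis.

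The second argument concerns size. A shortfall is conservative, so nothing claimed about type I error is broken. The analyses are event-driven, and no section provides for a final analysis 5% short. Near the target the loss is slight: at 331 DFS events cumulative alpha is 0.0248. The final DFS test takes place only if DFS was not rejected at IA1, where the stated power is 0.8402. All of this stands. It limits the weight of the point without removing it, particularly for OS.

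**Conclusion.** The point holds for a shortfall at the final analysis. The sSAP rule as written leaves alpha unspent and makes the last test needlessly strict. At a hazard ratio of 0.67 the cost is about 0.9 points of OS power at 196 deaths and 2.4 points at 190, and about 0.3 points of DFS power at 325 events and 1 point at 315. The figures assume earlier looks at the planned counts and proportional hazards. The shortfalls are illustrations, since the documents do not say how far the final counts may depart from target.

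A reader might go further and infer that the rule breaks the 2.5% control whenever the final count exceeds 332 or 200. The documents do not support that. It requires extrapolating the formula past an information fraction of 1, which the text neither directs nor rules out and which conflicts with the stated 2.5% level for each hypothesis. A cap at t = 1 is equally unstated, but it gives exactly 0.0250. The over-run is a second reason to make the sentence explicit; it is not a demonstrated loss of type I error control.

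**What to change.** In sSAP 3.8.1, limit the observed-over-planned rule to the interim analyses and add: *At the final analysis of each endpoint all remaining alpha is spent, so that cumulative one-sided alpha equals 0.025 whatever the observed number of events; the final bound is computed from the actual event counts at all analyses.* This settles both shortfall and over-run.

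Mirror the sentence in protocol 10.8.1 at the next amendment. If the sponsor regards it as a change of method for the primary or key secondary hypothesis rather than a clarification, the opening of protocol Section 10 requires an amendment. The cost is a wording change with its document control. It should be made before the final analyses, so that the choice cannot appear to depend on the final counts or results.
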